6.1.1.3. Retrospective Positive Sterility Findings from Prepared Study Intervention

If a positive sterility finding occurs in the terminally sterile filtered study intervention, the participants who were dosed from the impacted batch should be contacted immediately and undergo a full physical examination including, but not limited to, BP, pulse rate, and body temperature.

A blood sample should be collected for culture and assayed for inflammatory markers such as C-reactive protein and elevations in white blood cell counts.

If the signs and symptoms indicated a participant has a possible infection, they will be clinically managed, treated, and followed up until resolution. Any AEs will be recorded as appropriate.

6.2. Preparation/Handling/Storage/Accountability

The investigator or designee must confirm appropriate temperature conditions have been maintained during transit for all study interventions received and any discrepancies are reported and resolved before use of the study intervention.

To protect blinding, the interventions must be prepared by unblinded site personnel qualified to prepare study intervention who are not involved in any other study-related procedures. Instructions for preparation will be provided by the sponsor.

Only participants enrolled in the study may receive study intervention and only authorized site personnel may supply or administer study intervention. All study interventions must be stored in a secure, environmentally controlled, and monitored (manual or automated) area in accordance with the labeled storage conditions with access limited to the investigator and authorized site personnel.

The investigator, institution, or the head of the medical institution (where applicable) is responsible for study intervention accountability, reconciliation, and record maintenance (i.e., receipt, reconciliation, and final disposition records).

Further guidance and information for the final disposition of unused study interventions are provided in the pharmacy manual.

6.3. Measures to Minimize Bias: Randomization and Blinding

Randomization tables for allocation of either LY3832479 or placebo will be prepared by the statistician or their designee.

Blinding will be maintained throughout the conduct of the study as described in the separate Blinding Plan.

Emergency codes will be available to the investigator. A code, which reveals the treatment group for a specific study subject, may be opened during the study only if the subject's well-being requires knowledge of the subject's treatment assignment.

In case of an emergency, the investigator has the sole responsibility for determining if unblinding of a subject's treatment assignment is warranted for medical management of the event. The subject's safety must always be the first consideration in making such a determination. If the investigator decides that unblinding is warranted, it is the responsibility of the investigator to promptly document the decision and rationale and notify Lilly as soon as possible.

If an investigator, site personnel performing assessments, or participant is unblinded while the infusion is ongoing, the participant must be discontinued from the study intervention and the infusion stopped. If any amount of study intervention was administered, follow procedures according to the SoA as described in Section 7.1.

Upon completion of the study, all codes must be returned to Lilly or its designee.

6.4. Study Intervention Compliance

Participants will receive study intervention directly from the investigator or designee, under medical supervision. The date and time of each dose administered in the clinic will be recorded in the source documents and recorded in the CRF. The dose of study intervention and study participant identification will be confirmed at the time of dosing by a member of the study site personnel other than the person administering the study intervention.

6.5. Concomitant Therapy

All concomitant medications, whether prescription or over the counter, used at baseline and/or during the course of the trial, must be recorded on the Concomitant Medication electronic case report form (eCRF). Participants will be instructed to consult the investigator or other appropriate study personnel at the study site before taking any new medications or supplements during the study.

In general, concomitant medication should be avoided. Use of chronic, stable doses of hormone replacement therapy, thyroid replacement medications, or vitamin and mineral supplements is allowed. Acetaminophen (1 g, maximum 3 g/24 hours) may be administered at the discretion of the investigator for treatment of headache, etc.

If the need for concomitant medication (other than acetaminophen) arises, inclusion or continuation of the participant may be at the discretion of the investigator after consultation with a Lilly clinical pharmacologist or clinical research physician (CRP).

Any medication used during the course of the study must be documented.

All vaccines are prohibited until study completion.

6.6. Dose Modification

Depending on the results of a given trial-level safety review, the dose of the subsequent cohort(s) may be adjusted. Because these adjustments to dose levels are allowable changes permitted by the protocol, they would not require a protocol amendment.

6.6.1. Dose-Escalation Criteria

By nature of being a Phase 1 sponsor unblinded dose-escalation study, data will be evaluated on an ongoing basis until the highest planned dose has been administered.

After at least 7 participants have completed Day 4 in a given cohort, all safety data up to this cutoff date will be reviewed to determine whether the next cohort can be randomized after agreement between Lilly's medical monitor and the investigator. Safety and tolerability data will be the primary criteria guiding dose escalation.

The investigator and the Lilly sponsor team are responsible for determining any dose decisions. The investigator(s) will remain blinded and the Lilly sponsor team will be unblinded during these reviews. All available data from previous cohorts will be reviewed.

If temporary stopping criteria are met (Section 6.6.3), dosing will be temporarily halted and no further participants will be dosed until a full safety review of the study has taken place.

6.6.2. Access to Data during the Study

A limited number of unblinded Lilly study team personnel will have access to safety and/or PK data during the study.

6.6.3. Temporary Stopping Criteria

Dosing will be temporarily halted, and no further participants will be dosed until safety data available at that point have been reviewed, if

- 3 or more participants develop AEs that are considered to be related to study treatment and graded as at least moderate, clinically significant, and not responsive to supportive care.
- 1 or more participants develop AEs that are considered to be related to study treatment and that are serious (serious adverse events [SAEs]) or graded as severe.

This table describes the location of AE-related information in this protocol.

Topic	Location
DAIDS table describing severity of reactions	Section 6.1.1.2
Definition of AEs	Section 10.3.1
Assessment of Intensity/Severity	Section 10.3.3

Changes to the planned dosing schedule must be appropriately documented and communicated with the study personnel and the institutional review board (IRB)/independent ethics committee (IEC) before dosing continues.

6.7. Intervention after the End of the Study

Not applicable.

7. Discontinuation of Study Intervention and Participant Discontinuation/Withdrawal

These sections describe reasons for a participant's

- permanent or temporary discontinuation of study drug, or
- discontinuation (withdrawal) from the study.

Discontinuation of specific sites or of the trial as a whole are handled as part of regulatory, ethical, and trial oversight considerations in Section 10.1 Appendix 1.

7.1. Discontinuation of Study Intervention

In rare instances, it may be necessary for a participant to permanently discontinue study intervention. If the IV infusion is permanently stopped, the participant will remain in the study for follow-up and further evaluations as described in the SoA.

7.2. Participant Discontinuation/Withdrawal from the Study

A participant may withdraw from the study

- at any time at his/her own request
- at the request of his/her designee (for example, parents or legal guardian)
- at the discretion of the investigator for safety, behavioral, compliance, or administrative reasons
- if the participant becomes pregnant during the study
- if enrollment in any other clinical study involving an investigational product or enrollment in any other type of medical research judged not to be scientifically or medically compatible with this study

At the time of discontinuing from the study, if possible, an early discontinuation visit should be conducted, as shown in the SoA. See SoA for data to be collected at the time of study discontinuation and follow-up and for any further evaluations that need to be completed. The participant will be permanently discontinued both from the study intervention and from the study at that time.

If the participant withdraws consent for disclosure of future information, the sponsor may retain and continue to use any data collected before such a withdrawal of consent. If a participant withdraws from the study, he/she may request destruction of any samples taken and not tested, and the investigator must document this in the site study records.

7.2.1. Discontinuation of Inadvertently Enrolled Participants

If the sponsor or investigator identifies a participant who did not meet enrollment criteria and was inadvertently enrolled, then the participant should be discontinued from study treatment and safety follow-up should be performed as outlined in

- Section 1.3 (SoA),
- Section 8.2 (Safety Assessments), and

- Section 8.3 (Adverse Events and Serious Adverse Events).

7.3. **Lost to Follow-up**

A participant will be considered lost to follow-up if he or she repeatedly fails to return for scheduled visits and is unable to be contacted by the study site. Site personnel are expected to make diligent attempts to contact participants who fail to return for a scheduled visit or were otherwise unable to be followed up by the site.

8. Study Assessments and Procedures

Study procedures and their timing are summarized in the SoA (Section 1.3).

Immediate safety concerns should be discussed with the sponsor immediately upon occurrence or awareness to determine if the participant should continue or discontinue study intervention.

Adherence to the study design requirements, including those specified in the SoA, is essential and required for study conduct.

All screening evaluations must be completed and reviewed to confirm that potential participants meet all eligibility criteria. The investigator or designee will maintain a screening log to record details of all participants screened and to confirm eligibility or record reasons for screening failure, as applicable.

8.1. Efficacy Assessments

Not applicable.

8.2. Safety Assessments

Planned time points for all safety assessments are provided in the SoA.

8.2.1. Vital Signs

For each participant, vital sign measurements should be conducted according to the SoA (Section 1.3). Additional vital signs may be measured during each study period at the investigator's judgment. Blood pressure and pulse rate should be measured after at least 5 minutes supine.

Orthostatic vital signs should be assessed, if possible, during any AE of dizziness or posture-induced symptoms. If orthostatic measurements are required, participants should be supine for at least 5 minutes and stand for at least 3 minutes. If the participant feels unable to stand, supine vital signs only will be recorded.

Additional vital signs may be measured during each study period if warranted.

8.2.2. Electrocardiograms

Single 12-lead ECG readings will be obtained as outlined in the SoA (see Section 1.3).

Electrocardiograms should be recorded before collecting any blood for safety or PK tests. Subjects must be supine for approximately 5 to 10 minutes before ECG collection and remain supine but awake during ECG collection.

Paper copies of all ECGs recorded should be stored at the investigational site.

Electrocardiograms may be obtained at additional times, when deemed clinically necessary. Collection of additional ECGs at a particular time point is allowed to ensure high-quality records. Electrocardiograms will be interpreted by a qualified physician (the investigator or qualified designee) at the study site as soon after the time of ECG collection as possible, and ideally while the subject is still present, to determine whether the subject meets entry criteria at

the relevant visit(s) and for immediate subject management, should any clinically relevant findings be identified.

Any clinically significant findings from ECGs that result in a diagnosis and that occur after the subject receives the investigational product should be reported to Lilly, or its designee, as an AE via the eCRF.

8.2.3. Clinical Safety Laboratory Assessments

See Section 10.2, Appendix 2 for the list of clinical laboratory tests to be performed and to the SoA for the timing and frequency.

All protocol-required laboratory assessments, as defined in Appendix 2, must be conducted in accordance with the laboratory manual and the SoA.

The investigator must review the laboratory report, document this review, and record any clinically relevant changes occurring during the study in the AE section of the CRF. The laboratory reports must be filed with the source documents.

If laboratory values from nonprotocol-specified laboratory assessments performed at the institution's local laboratory require a change in participant management or are considered clinically significant by the investigator (e.g., SAE or AE or dose modification), then the results must be recorded in the CRF.

8.2.4. Hepatic Monitoring

Close hepatic monitoring

Laboratory tests (Appendix 6, Section 10.6), including ALT, AST, ALP, TBL, D. Bil, GGT, and CK, should be repeated within 48 to 72 hours to confirm the abnormality and to determine if it is increasing or decreasing, if one or more of these conditions occur:

If a participant with baseline results of ...	develops the following elevations:
ALT or AST <1.5x ULN	ALT or AST ≥3x ULN
ALP <1.5x ULN	ALP ≥2x ULN
TBL <1.5x ULN	TBL ≥2x ULN (except for patients with Gilbert's syndrome)
ALT or AST ≥1.5x ULN	ALT or AST ≥2x baseline
ALP ≥1.5x ULN	ALP ≥2x baseline
TBL ≥1.5x ULN	TBL ≥2x baseline (except for patients with Gilbert's syndrome)

If the abnormality persists or worsens, clinical and laboratory monitoring, and evaluation for possible causes of abnormal liver tests should be initiated by the investigator in consultation with the Lilly-designated medical monitor. At a minimum, this evaluation should include physical examination and a thorough medical history, including symptoms, recent illnesses (for example, heart failure, systemic infection, hypotension, or seizures), recent travel, history of concomitant medications (including over-the-counter), herbal and dietary supplements, history of alcohol drinking and other substance abuse.

Initially, monitoring of symptoms and hepatic biochemical tests should be done at a frequency of 1 to 3 times weekly, based on the participant's clinical condition and hepatic biochemical tests. Subsequently, the frequency of monitoring may be lowered to once every 1 to 2 weeks, if the participant's clinical condition and lab results stabilize. Monitoring of ALT, AST, ALP, and TBL should continue until levels normalize or return to approximate baseline levels.

Comprehensive hepatic evaluation

A comprehensive evaluation should be performed to search for possible causes of liver injury if one or more of these conditions occur:

If a participant with baseline results of...	develops the following elevations:
ALT or AST <1.5x ULN	ALT or AST \geq 3x ULN with hepatic signs/symptoms*, or ALT or AST \geq 5x ULN
ALP <1.5x ULN	ALP \geq 3x ULN
TBL <1.5x ULN	TBL \geq 2x ULN (except for patients with Gilbert's syndrome)
ALT or AST \geq 1.5x ULN	ALT or AST \geq 2x baseline with hepatic signs/symptoms*, or ALT or AST \geq 3x baseline
ALP \geq 1.5x ULN	ALP \geq 2x baseline
TBL \geq 1.5x ULN	TBL \geq 1.5x baseline (except for patients with Gilbert's syndrome)

* Hepatic signs/symptoms are severe fatigue, nausea, vomiting, right upper quadrant abdominal pain, fever, rash, and/or eosinophilia >5%.

At a minimum, this evaluation should include physical examination and a thorough medical history, as outlined above, as well as tests for PT-INR; tests for viral hepatitis A, B, C, or E; tests for autoimmune hepatitis; and an abdominal imaging study (for example, ultrasound or CT scan).

Based on the patient's history and initial results, further testing should be considered in consultation with the Lilly-designated medical monitor, including tests for hepatitis D virus (HDV), cytomegalovirus (CMV), Epstein-Barr virus (EBV), acetaminophen levels, acetaminophen protein adducts, urine toxicology screen, Wilson's disease, blood alcohol levels, urinary ethyl glucuronide, and serum phosphatidylethanol. Based on the circumstances and the investigator's assessment of the participant's clinical condition, the investigator should consider referring the participant for a hepatologist or gastroenterologist consultation, magnetic resonance cholangiopancreatography (MRCP), endoscopic retrograde cholangiopancreatography (ERCP), cardiac echocardiogram, or a liver biopsy.

Additional hepatic data collection (hepatic safety CRF) in study participants who have abnormal liver tests during the study

Additional hepatic safety data collection in hepatic safety case report forms (CRF) should be performed in study participants who meet 1 or more of the following 5 conditions:

1. Elevation of serum ALT to ≥ 5 x ULN on 2 or more consecutive blood tests (if baseline ALT < 1.5 x ULN)
 - In participants with baseline ALT ≥ 1.5 x ULN, the threshold is ALT ≥ 3 x baseline on 2 or more consecutive tests
2. Elevated TBL to ≥ 2 x ULN (if baseline TBL < 1.5 x ULN) (except for cases of known Gilbert's syndrome)
 - In participants with baseline TBL ≥ 1.5 x ULN, the threshold should be TBL ≥ 2 x baseline
3. Elevation of serum ALP to ≥ 2 x ULN on 2 or more consecutive blood tests (if baseline ALP < 1.5 x ULN)
 - In participants with baseline ALP ≥ 1.5 x ULN, the threshold is ALP ≥ 2 x baseline on 2 or more consecutive blood tests
4. Hepatic event considered to be a serious adverse event (SAE)
5. Discontinuation of study drug due to a hepatic event.

Note: the interval between the two consecutive blood tests should be at least 2 days.

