9.4.6 Hepatic Monitoring

If a subject experiences elevated alanine aminotransferase (ALT) or aspartate aminotransferase (AST) $\geq 3 \times$ upper limit of normal (ULN), alkaline phosphatase (ALP) $\geq 2 \times$ ULN, or elevated total bilirubin (TBL) $\geq 2 \times$ ULN, liver tests will be performed to confirm the abnormality. Additional safety data may be collected if required, as defined in the protocol. Where applicable, the following will be presented.

The subjects' liver disease history and associated person liver disease history data will be listed. Any concomitant medications that have potential for hepatotoxicity, including acetaminophen will be listed. Results from any hepatic monitoring procedures, such as a magnetic resonance elastography (MRE) scan, and biopsy assessments will be listed, if performed.

Hepatic risk factor assessment data will be listed. Liver related signs and symptoms data will be summarized by treatment and listed. Alcohol and recreational drug use data will also be listed.

All hepatic chemistry, hematology, coagulation, and serology data will be listed. Values outside the reference ranges will be flagged on the individual subject data listings.

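### With raised baseline bilirubin, the comprehensive liver work-up starts at 1.5x baseline but the timed repeat test only at 2x baseline, reversing the order of the two tiers

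*Protocol*

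**What the plan says.** Protocol 8.2.4 (Hepatic Monitoring) has two trigger tables, each with six rows: ALT/AST, ALP and TBL, split by whether the baseline value is below 1.5x ULN or at least 1.5x ULN.

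- **Close hepatic monitoring.** When a row is met, the liver tests "should be repeated within 48 to 72 hours to confirm the abnormality and to determine if it is increasing or decreasing". If the abnormality persists or worsens, "monitoring of symptoms and hepatic biochemical tests should be done at a frequency of 1 to 3 times weekly" at first. For baseline TBL of at least 1.5x ULN, the trigger is "TBL ≥2x baseline (except for patients with Gilbert's syndrome").
- **Comprehensive hepatic evaluation.** When a row is met, possible causes of liver injury are to be sought. The minimum content is a physical examination, a history, PT-INR, viral hepatitis tests, "tests for autoimmune hepatitis; and an abdominal imaging study". For baseline TBL of at least 1.5x ULN, the trigger is TBL of at least "1.5x baseline (except for patients with Gilbert's syndrome").

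The same section sets a third TBL threshold, for completing the additional hepatic safety CRF. It is 2x ULN if baseline TBL is below 1.5x ULN, and 2x baseline otherwise.

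**The concern.** The two tiers read as a ladder. The first step is a cheap repeat blood test to see whether the value is real and which way it is moving. The second is a fuller search for a cause. One expects the first step to start at or below the second. In the raised-baseline TBL row it starts above it.

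A participant in the range between the two triggers is therefore due hepatitis serology and abdominal imaging. On TBL alone, that participant is not due the timed repeat or the monitoring 1 to 3 times weekly that would follow a persistent rise. The minimum content of the work-up lists no timed repeat either. What is at stake is a small gap in a participant-safety rule. No estimate, test or summary depends on it.

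**Working it through.** **Step 1: compare the tiers row by row.** Both columns come from the tables in Protocol 8.2.4. The work-up column is the trigger without hepatic signs or symptoms.

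| Baseline row | Repeat trigger | Work-up trigger | Work-up relative to repeat |
|---|---|---|---|
| ALT/AST <1.5x ULN | 3x ULN | 5x ULN | higher |
| ALP <1.5x ULN | 2x ULN | 3x ULN | higher |
| TBL <1.5x ULN | 2x ULN | 2x ULN | equal |
| ALT/AST ≥1.5x ULN | 2x baseline | 3x baseline | higher |
| ALP ≥1.5x ULN | 2x baseline | 2x baseline | equal |
| TBL ≥1.5x ULN | 2x baseline | 1.5x baseline | **lower** |

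The work-up trigger is higher in three rows, equal in two and lower in one. With symptoms, the ALT/AST work-up triggers fall to 3x ULN and 2x baseline. These equal the repeat triggers, so no further row is reversed.

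**Step 2: size of the gap.** For a baseline of b × ULN, the work-up starts at 1.5b and the repeat at 2b. The gap runs from 1.5b to below 2b, with width 0.5b.

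- b = 1.5: 1.5 × 1.5 = 2.25 and 2 × 1.5 = 3.0, so the gap is 2.25x to below 3.0x ULN (width 0.75x ULN).
- b = 2.0: 1.5 × 2.0 = 3.0 and 2 × 2.0 = 4.0, so the gap is 3.0x to below 4.0x ULN (width 1.0x ULN).

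**Step 3: what the schedule supplies instead.** The nominal follow-up days in the Schedule of Activities are 8, 15, 22, 29, 43, 57, 71 and 85. Successive differences are 7, 7, 7, 14, 14, 14 and 14 days, against 2 to 3 days for the timed repeat. Day 85 is the last scheduled visit.

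**Step 4: which cell is out of line.** For baseline TBL below 1.5x ULN, the repeat, work-up and CRF thresholds are all 2x ULN. For baseline TBL of at least 1.5x ULN, they are 2x, 1.5x and 2x baseline. The 1.5x cell is the odd one of the three. That is suggestive but not conclusive, because the CRF threshold does not always follow the work-up trigger. For ALP below 1.5x ULN, the CRF threshold is 2x ULN (on consecutive tests) and the work-up trigger is 3x ULN.

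**Step 5: effect of the fix.** With the last repeat cell at 1.5x baseline, the work-up trigger is higher in three rows, equal in three and lower in none.

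**The case against.** The strongest objection is that the 1.5x work-up cell may be the slip. The repeat and CRF thresholds for this group agree at 2x baseline, so changing the repeat cell departs from the majority and leaves the CRF at 2x. This stands as far as intent goes: the documents do not settle which cell was meant. It does not remove the reversal. Raising the work-up cell to 2x would also restore the order, but only by relaxing a safety trigger. The CRF threshold governs extra data collection and can stay where it is.

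The second objection is that the gap is largely covered, and much of this stands. Appendix 6 lists total and direct bilirubin in the hepatic evaluation panel, so a work-up may well include a repeat value, although no timing is set. Appendix 2 allows additional tests at any time, and Appendix 3 obliges the investigator to arrange supplemental measurements for an AE as medically indicated. A reader might infer that a participant in the gap goes unevaluated. That is not so: the more intensive step still applies, and no row makes it wait for a repeat.

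Two further arguments may tempt a reader, and neither supports the point.

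- **A specific conflict with the SAP.** SAP 9.4.6 says that, at TBL of at least 2x ULN whatever the baseline, "liver tests will be performed to confirm the abnormality". Its ULN-only wording departs from the protocol in other rows too. At baseline ALP 1.5x ULN, the protocol repeat starts at 2 × 1.5 = 3.0x ULN and the SAP's at 2x ULN. The difference would also survive the fix: at baseline TBL 2.0x ULN, the protocol repeat would start at 1.5 × 2.0 = 3.0x ULN, against 2x ULN in the SAP.
- **An anomalous jump at the baseline cut-off.** The TBL repeat trigger steps from 2.0x to 3.0x ULN at a baseline of 1.5x ULN. The ALP repeat trigger makes the same step, so this does not single out the TBL row.

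**Conclusion.** The concern holds as a minor internal inconsistency in a safety rule. In the row for baseline TBL of at least 1.5x ULN, the work-up trigger lies below the repeat trigger, and no other row does this. A rise of 1.5x to below 2x baseline calls for serology and imaging without, on TBL alone, a timed repeat. The qualification matters: a simultaneous rise in ALT, AST or ALP could trigger the repeat through its own row.

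Few if any participants would be affected. The gap needs a non-Gilbert's participant with baseline TBL of at least 1.5x ULN among at most 30 healthy volunteers. Inclusion criterion 3 allows that only if the investigator judges the result not clinically significant, and TBL must then rise by at least 50% but less than 100%. The documents give no frequency for this, so few if any is a judgement. No stopping rule, dose-escalation criterion or planned analysis uses the cut-off.

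**What to change.** In the close hepatic monitoring table of Protocol 8.2.4, change the trigger for baseline TBL of at least 1.5x ULN from 2x baseline to 1.5x baseline, and keep the Gilbert's exception. Leave the comprehensive evaluation trigger at 1.5x baseline and the hepatic safety CRF threshold at 2x baseline. The two tiers are then equal in this row, as they already are for TBL below 1.5x ULN and for ALP of at least 1.5x ULN, and no safety trigger is relaxed.

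The cost is one table cell, which can wait for the next amendment. In use, the downside is an occasional extra blood test, with monitoring 1 to 3 times weekly if the rise persists, in a participant who is already due the full work-up.
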